### Imputation

Subjects with a missing baseline assessment or no post-baseline assessment of CRP will not be imputed and will not be included in the analysis.

Post-baseline assessments up to and including the next non-missing assessment (including those at or after the withdrawal assessment) following the final treatment administration will be considered as the treatment period for inclusion in the mean. The mean of their last two non-missing scheduled assessments during the treatment period, or a single CRP value where the subject has only completed one post-baseline CRP assessment, will be carried forward to represent state at the end of trial.

### Summaries

Descriptive statistics will summarise the CRP values and change from baseline at each assessment for each study treatment. The geometric mean, SD on the log scale and % coefficient of variation (CV) will also be presented. CRP values including the change from baseline will be listed.

### Sensitivity Analysis

A sensitivity analysis will be conducted using the mean of the last two non-missing post-baseline values during the treatment and follow-up periods (up to and including Visit 9). If there is only one post-baseline value then this value will be used. This approach is expected to be conservative as it includes a time period when patients in the active treatment arm are potentially untreated.

The analysis will be a repeat of the ANCOVA described above.

Further sensitivity analyses may be considered post-hoc.

## **6.10.2 Secondary Endpoints**

All secondary efficacy endpoints will be analyzed and summarized using the FAS as the primary analysis set.

### **6.10.2.1 Change from Baseline in Body Temperature and Laboratory Values**

#### Analysis

The change from baseline in body temperature, cytokines (IL-6, IL-10 and TNF), CA125 and ferritin will be analysed using the model outlined for the primary endpoint in Section 6.10.1 of this SAP.

In each case, the change in each parameter from baseline to the mean of the last two non-missing scheduled assessments during the treatment period will be analysed using an ANCOVA. For subjects who do not complete treatment, the assessments up to and including the assessment on the day of last study treatment administration will be considered for inclusion in the mean. The model will be fitted with the change from baseline as the dependent variable and study treatment as a fixed effect. The baseline value will be included as a covariate. Model assumptions will be checked and data transformations will be applied as described in Section 6.10.1.

These analyses will be reported as described for the primary endpoint in Section 6.10.1.

#### Imputation

Data will be imputed for each parameter as detailed in Section 6.10.1 for the primary endpoint. For subjects who have no post-baseline assessments, no imputation will be applied and they will be excluded from the analysis.

#### Summaries

Descriptive statistics for observed and change from baseline values of each parameter will be provided at each assessment for each study treatment as outlined for the primary endpoint. Listings of each parameter will be provided including the change from baseline.

### **6.10.2.2 Number of Subjects Not in Need of Oxygen Supply**

A subject will be deemed to not need oxygen if they did not receive supplemental oxygen on their last day of study treatment administration, as recorded on the Supplemental Oxygen eCRF page.

#### Analysis

The proportion of subjects not in need of oxygen supply at their last study treatment administration visit will be analysed using a logistic regression model. The model will be fitted with oxygen required (Yes/No) as the dependent variable and study treatment as a fixed effect. The number and percentage of subjects not requiring oxygen, together with the proportion of subjects not requiring oxygen and the Clopper-Pearson 90% CI for the proportion, will be presented for each dose group. The odds ratio, associated 90% CI and two-sided p-value will also be presented.

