### 6.2.1 Definition of Baseline

The derivation of baseline for CRP is described in Section 6.10.1 of this SAP.

Baseline for all other variables is defined as the last non-missing value (including scheduled and unscheduled assessments) prior to the subject receiving study treatment. For assessments performed at Visit 2 where it is not clear that the assessment was performed after study treatment administration, the assessment will be taken as a post-baseline assessment.

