### Sensitivity Analysis

A sensitivity analysis will be performed including subjects who have no post-baseline assessments. These subjects will be assumed to require oxygen if they received C21 and assumed not to require oxygen if they received placebo.

The logistic regression model described above will be repeated.

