### **6.10.2.5 Time on Oxygen Supply**

The time on oxygen supply is defined as the number of calendar days on which a subject was recorded as receiving oxygen on the Supplemental Oxygen eCRF page from Visit 2 to Visit 8. For subjects who do not complete treatment, the assessments up to and including the day of the last study treatment administration will be considered and remaining assessments will be imputed as described below. Therefore, a discrete number of responses are available from 0 days to 7 days. Subjects are deemed to have received oxygen where it has been administered at any time for any duration on the date of each visit.

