## Analysis

A comparison between the two study treatments will be performed using a Wilcoxon rank sum test. A two-sided p-value of the treatment difference will be presented.

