## Imputations

The treatment period for each subject is defined as from the date of first study treatment administration to the date of last study treatment administration. Where subjects have been withdrawn from treatment with the reason for withdrawal recorded as need for mechanical invasive or non-invasive ventilation, or they record need for ventilation (per the mechanical ventilation eCRF page) on the day of last study treatment administration, they will be assumed to require oxygen for the day of withdrawal / last study treatment administration and all subsequent visits up to and including Visit 8 regardless of the oxygen requirement information entered into the Supplemental Oxygen eCRF page. Similarly if a subject withdraws due to death or dies on the day of last study treatment administration they will be assumed to require

oxygen for the day of death and all subsequent visits up to and including Visit 8 regardless of the oxygen requirement entered into the Supplemental Oxygen eCRF page. Otherwise, if a subject has missing assessments for any other reason, their last known oxygen status prior to the missing assessment will be carried forward for the analysis. For subjects who have no post-baseline assessments, no imputation will be applied and they will be excluded from the analysis.

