5.4.1 Withdrawal from Trial IMP

If a subject is prematurely withdrawn from IMP, the Investigator must make every effort to perform the withdrawal assessments described in Section 6.5.3, and further perform end-of-trial Visit (Visit 9) 7-10 days after the last dose of IMP.

A subject will be withdrawn from IMP if any of the following occurs:

- Need for mechanical invasive or non-invasive ventilation
- Discharge from the hospital/controlled facility
- Major protocol deviations as defined by Sponsor.

Vicore Pharma AB Version: 2.0 Trial ID: VP-C21-006 Date: 14-Aug-2020

• Sponsor decision to stop the trial or to stop the subject's participation in the trial; reasons may include medical, safety, or regulatory issues, or other reasons consistent with applicable laws, regulations, and GCP.

- It is the wish of the subject for any reason
- The Investigator judges it necessary due to medical reasons
- Adverse events such as:
 - Serious cardiovascular complications such as severe peripheral oedema or significant bradycardia indicating a potential risk for the subject as evaluated by the Investigator
 - o Moderate to severe skin rashes as judged by the Investigator e.g. Stevens-Johnson syndrome and toxic epidermal necrolysis
- Pregnancy

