6.5.2 Treatment Period (Visits 2-8)

The treatment period lasts for 7 days (Visit 2-8). The procedures to be performed at each visit are specified below.

Vicore Pharma AB Version: 2.0 Trial ID: VP-C21-006 Date: 14-Aug-2020

Visit 2

Visit 2 can be scheduled as soon as the relevant screening assessments are available. Visit 2 must occur within 3 days from Visit 1 (screening).

The following procedures are performed:

- Re-evaluation of in- & exclusion criteria
- Short physical examination (including vital signs)
- Evaluation of ECG and laboratory results from Visit 1
- Assignment of randomisation number
- Concomitant medication
- Recording need of supplementary O₂
- Blood sampling for:
 - o CRP
 - Safety (haematology and biochemistry) (see Section 8.2.7)
 - o IL-6, IL-10, TNF, CA125, ferritin
 - o Biomarkers
- Urinalysis (dipstick for bilirubin, glucose, ketones, protein, specific gravity, urobilinogen and pH)
- IMP administration twice daily including diatery restrictions (see Section 5.3.2)
- Check of withdrawal criteria
- Adverse events

Visits 3-8

- Concomitant medication
- Short physical examination (including vital signs at the judgement of the Investigator)
- Recording need of supplementary O₂
- Blood sampling for
 - o CRP
 - o Safety (haematology and biochemistry) (see Section 8.2.7)
 - o IL-6, IL-10, TNF, CA125, ferritin
- Urinalysis (dipstick for bilirubin, glucose, ketones, protein, specific gravity, urobilinogen and pH)
- IMP administration twice daily including dietary restrictions (see Section 5.3.2)
- Check of withdrawal criteria
- Adverse events

In addition for Visit 8 (end-of-treatment) only:

- Pregnancy testing (urine dip-stick), if positive a blood pregnancy test must be performed to confirm positive pregnancy
- Biomarkers
- Drug accountability

Vicore Pharma AB Version: 2.0 Trial ID: VP-C21-006 Date: 14-Aug-2020

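### Neither oxygen comparison uses baseline oxygen status, which can cost power and leaves chance imbalance uncorrected; a low-severity, inexpensive improvement

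*SAP*

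**What the plan says.** **Last-day oxygen need (SAP 6.10.2.2).** "The model will be fitted with oxygen required (Yes/No) as the dependent variable and study treatment as a fixed effect". The sensitivity analysis changes who is included but not the model: "The logistic regression model described above will be repeated". Protocol 13.3.1 also names treatment as the only term.

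**Days on oxygen (SAP 6.10.2.5).** "A comparison between the two study treatments will be performed using a Wilcoxon rank sum test". No stratification is given.

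**Baseline oxygen elsewhere in the plan.** It is recorded at Visits 1 and 2 (protocol Table 1), tabulated in SAP 6.7.1, and used as a Yes/No subgroup factor for CRP in SAP 6.10.6. That section leaves the same subgroups optional for secondary endpoints. SAP 6.10.2.1 includes the baseline value as a covariate for each continuous secondary endpoint.

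**Other relevant provisions.** Randomisation is 1:1 with no stratification factor described (SAP 4). Country may enter the models if more than 10 subjects are recruited per country (SAP 6.10.5). Secondary endpoints are descriptive, without multiplicity control (SAP 6.10.4).

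**The concern.** Whether a patient is on oxygen at the start is a natural predictor of whether that patient is on oxygen on the last day, and for how many of seven days. If it does predict, leaving it out has two costs.

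- **Power.** Variation that baseline status could explain stays in the comparison.
- **Interpretation.** With unstratified allocation the arms can start with different oxygen use by chance. The demography table would show this, but no planned analysis would correct it, and a correction chosen after unblinding would be post hoc.

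The SAP already applies the principle to every continuous secondary endpoint. Country, the only other covariate foreseen, does not stand in for oxygen status.

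**Working it through.** **1. Inputs from the documents.** 75 per arm (SAP 2.3); two-sided 10% with 90% intervals (SAP 6.1). No oxygen prevalence, last-day rate or power is given for either endpoint. The only stated power is for CRP, and it reproduces: 25 / (60 × √(2/75)) = 25 / 9.80 = 2.55; 2.55 − 1.645 = 0.907; power 81.8%, against about 80% stated. It says nothing about oxygen.

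**2. Assumptions.** 30, 50 or 70% on oxygen at baseline; conditional odds ratio 0.4; four sets of placebo last-day oxygen rates for patients on versus off oxygen at baseline.

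**3. One logistic scenario by hand** (60% vs 10%, half on oxygen at baseline). An odds ratio of 0.4 gives C21 rates of 37.5% and 4.26%, so the overall rates are 35.0% (placebo) and 20.9% (C21).

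- Treatment only: log-OR = ln(0.490) = −0.713; SE = √[1/(75×0.350×0.650) + 1/(75×0.209×0.791)] = 0.373; 0.713/0.373 − 1.645 = 0.27; power about 60%.
- With baseline oxygen (37.5 per arm and stratum): information is 1/(1/9.00 + 1/8.79) = 4.45 (on oxygen) plus 1/(1/3.375 + 1/1.53) = 1.05 (off oxygen); SE = 1/√5.50 = 0.426; 0.916/0.426 − 1.645 = 0.50; power about 69%.

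The SE rises, but the log-OR moves further from zero, so power rises.

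**4. Simulation of all four scenarios** (20,000 trials each). The first column of gains covers 30–70% prevalence; the other columns are at 50%.

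| Placebo rate, on vs off | Power gain (points) | Power, crude → adjusted | log-OR SE, crude → conditional | Risk-difference SE (points), crude → standardised |
|---|---|---|---|---|
| 35% vs 25% | 0 | 73 → 73% | 0.416 → 0.421 | 6.7 → 6.6 |
| 50% vs 20% | 2–3 | 73 → 76% | 0.384 → 0.406 | 7.1 → 6.8 |
| 60% vs 10% | 5–10 | 60 → 70% | 0.376 → 0.434 | 7.2 → 6.3 |
| 70% vs 5% | 11–16 | 49 → 65% | 0.359 → 0.464 | 7.5 → 5.9 |

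At 50% prevalence the conditional odds-ratio interval is therefore 1–29% wider on the log scale (about 35% at 30% prevalence in the last scenario). The standardised risk-difference interval is 1–21% narrower.

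**5. Which baseline record can be used.** For days on oxygen, the Visit 2 date belongs to the outcome: "Subjects are deemed to have received oxygen where it has been administered at any time for any duration on the date of each visit". For Visit 2 assessments, SAP 6.2.1 adds: "where it is not clear that the assessment was performed after study treatment administration, the assessment will be taken as a post-baseline assessment". Unless a Visit 2 record is clearly pre-dose, the baseline is Visit 1, up to 3 days earlier (protocol 6.5.2).

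**6. Days on oxygen.** A daily stop/start model was run with withdrawal, because "Discharge from the hospital/controlled facility" ends treatment under protocol 5.4.1. Ventilation or death counts as on oxygen to Visit 8; otherwise "their last known oxygen status prior to the missing assessment will be carried forward for the analysis". Assumed daily withdrawal was 10 or 25% discharge while off oxygen, 2 or 4% ventilation or death while on it, and 1 or 2% for other reasons. C21 was assumed to multiply the odds of stopping oxygen by 1.4, 1.6, 2 and 2 in the four rows, and to divide the odds of starting by the same factor. Gain of van Elteren over Wilcoxon, in power points:

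| Placebo daily chance of stopping / starting | Status 3 days old | 1 day old | Clearly pre-dose at Visit 2 |
|---|---|---|---|
| 55 / 45% | 0 | 0 | 0–1 |
| 45 / 25% | 0 | 0 | 3–6 |
| 20 / 5% | 5–6 | 16–20 | 22–36 |
| 10 / 2% | 11–15 | 21–29 | 31–42 |

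In the same model with a 3-day-old status, the logistic gain is −0.4 to +5.3 points.

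**7. Chance imbalance.** The SD of the between-arm difference is √(2π(1−π)/75), where π is the share on oxygen at baseline: 7.5 points at 30 or 70%, 8.2 at 50%. A difference of at least 10 points means 8 or more subjects (8/75 = 10.7 points); its exact binomial probability is 18.1, 22.1 and 18.1% at 30, 50 and 70%. In those trials, with no drug effect, the unadjusted logistic test rejects in 10–29% against 9–10% adjusted. The Wilcoxon test rejects in 9–27% against 9–13% for van Elteren (3-day-old status). Over all trials every method rejects in about 9–12%.

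**The case against.** The strongest reply is that nothing here is wrong. The tests hold their level, the SAP follows the protocol, and no confirmatory claim rests on descriptive secondary endpoints. That is correct and is why the severity is low. It does not remove the point: odds ratios, intervals and p-values will be reported, and protocol 3.6 says the data will guide later trials.

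Second, every size comes from assumed rates, and the gains run from zero to 42 points. This also stands. The largest gains need a clearly pre-dose Visit 2 record, which a whole-day oxygen record may not supply. The 3-day-old Visit 1 results are the cautious guide.

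Third, adjustment changes the meaning of the odds ratio and widens its interval. This is true, and it is the reason to report a standardised estimate alongside.

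Fourth, an imbalance would be visible: SAP 6.7.1 tabulates baseline oxygen, the summaries in 6.10.2.5 show oxygen days during screening, and 6.10.6 allows subgroup exploration. These display or explore an imbalance; none adjusts for it.

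**Conclusion.** The point holds as a low-severity improvement. Neither oxygen comparison uses a baseline value that the trial already collects, in contrast with the SAP's own handling of the continuous secondary endpoints. The planned tests are valid, and the primary CRP analysis is unaffected.

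The benefit is negligible if baseline oxygen is weakly prognostic and useful if it is strongly prognostic; the documents do not allow a choice between these cases. The surer gain is a prespecified answer in the roughly one trial in five that starts with a 10-point imbalance. Confidence in the sizes is medium, because they depend on the assumed rates, the withdrawal pattern and the age of the baseline record.

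**What to change.** Before database lock:

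1. Add baseline supplemental oxygen (Yes/No) to the logistic model in 6.10.2.2 and to its sensitivity repeat. State that the odds ratio is conditional. Add a standardised (marginal) risk difference or odds ratio with a 90% interval beside the crude proportions. Name Firth's penalised likelihood as the fallback when a baseline stratum has no events; in simulation this occurs in 0% of trials, at most 0.1%, 0.1–4% and 2–21% across the four scenarios. The same fallback should cover a stratum in which everyone needs oxygen.
2. Replace the Wilcoxon test in 6.10.2.5 with a van Elteren test stratified by baseline oxygen, and say how country (6.10.5) enters, if at all.
3. Define baseline oxygen as the last record clearly before first dose, never the whole-day Visit 2 record that counts in the outcome, and give a rule for a missing value.
4. Keep the unadjusted results as supportive and list the change from protocol 13.3.1 in SAP 6.12.

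**Cost.** SAP wording, one derived variable and one extra estimate; no new assessments. The conditional odds ratio will differ from the crude one and have a wider log-scale interval. A weak predictor costs at most about 1 power point, and using Firth throughout would cost at most 2. The standardised risk-difference test rejects in 10.4–10.9% under the null.

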#### Imputation

For subjects who have withdrawn from treatment due to a need for mechanical ventilation or due to death, or who require mechanical ventilation or die on their last day of study treatment administration, they will be assumed to require oxygen regardless of the oxygen requirement entered into the Supplemental Oxygen eCRF page. For subjects who withdraw from treatment for any other reason, their oxygen status on the last day of study treatment administration according to the Supplemental Oxygen eCRF page will be used. For subjects who have missing data not due to

withdrawal from treatment, their last known oxygen status prior to the missing assessment will be carried forward. For subjects who have no post-baseline assessments, no imputation will be applied and they will be excluded from the analysis.

### Sensitivity Analysis

A sensitivity analysis will be performed including subjects who have no post-baseline assessments. These subjects will be assumed to require oxygen if they received C21 and assumed not to require oxygen if they received placebo.

The logistic regression model described above will be repeated.

### **6.10.2.3 Number of Subjects Not in Need of Mechanical Invasive or Non-Invasive Ventilation**

The decision for a subject's need for mechanical ventilation (invasive or non-invasive) during the treatment period will determine their response for use in this analysis, irrespective of whether they subsequently received ventilation. A subject will be considered to need mechanical ventilation during the treatment period if they are withdrawn from treatment with the reason for withdrawal recorded as need for mechanical invasive or non-invasive ventilation or death. Any mechanical invasive or non-invasive ventilation or death recorded in the time between last treatment administration + 12 hours will also be considered an event. The treatment period for each subject is from the date and time of their first study treatment administration to the date and time of their last study treatment administration + 12 hours.

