### Analysis

The proportion of subjects not in need of mechanical ventilation (either invasive or non-invasive) at any point during the study treatment period will be analysed using a logistic regression model. The model will be fitted with ventilation required (Yes/No) as the dependent variable and study treatment as a fixed effect. The number and percentage of subjects not requiring ventilation, together with the proportion of subjects not requiring ventilation and the Clopper-Pearson 90% CI for the proportion, will be presented for each dose group. The odds ratio, associated 90% CI and two-sided p-value will also be presented.

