### Imputation

Where subjects have been withdrawn from treatment for a reason other than need for mechanical invasive or non-invasive ventilation or death, and have not recorded requirement for mechanical invasive or non-invasive ventilation or death during the time from last treatment administration + 12 hours, they will be considered not in need of mechanical ventilation during the treatment period. All subjects who commence treatment will have an End of Treatment eCRF page completed indicating whether or not the subject was withdrawn due to need for mechanical ventilation or death. Therefore, no further imputation is required.

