### Sensitivity Analysis

A sensitivity analysis will be performed including any additional information gathered between the last study treatment administration and Visit 9 (follow-up period), therefore this analysis will include all data collected from the first treatment administration to the date of study completion or withdrawal. The need for mechanical ventilation is not captured during the follow-up period however the start time of any mechanical ventilation is captured. Therefore, the sensitivity analysis will consider a subject to need mechanical ventilation during the study if any of the following are recorded from the date and time of first study treatment administration to the date of study completion/withdrawal:

- withdrawal from treatment with the reason for withdrawal recorded as need for mechanical invasive or non-invasive ventilation,
- any entry on the Mechanical Ventilation eCRF page indicating that ventilation was required,
- death as recorded on the adverse event or withdrawal from study pages.

The logistic regression model described above will be repeated.

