#### **6.10.2.4 Time to Need of Mechanical Invasive or Non-Invasive Ventilation**

Time to need of mechanical ventilation (invasive or non-invasive) for each subject is calculated in hours as (Date and time of decision for need of ventilation) – (Date and time of first administration of study treatment). The treatment period for each subject is from the date and time of their first study treatment administration to the date and time of their last study treatment administration + 12 hours. For subjects who withdraw from treatment with the reason for withdrawal as need for mechanical invasive or non-invasive ventilation, the date and time of decision for need of ventilation is taken from the date and time at which the subject withdrew from treatment (as recorded on the End of Treatment page of the eCRF). For subjects who do not withdraw from treatment due to need for mechanical invasive or non-invasive ventilation but who have an entry on the Mechanical Ventilation eCRF page indicating that ventilation was required during the treatment period, the start date and time from this page will be used to calculate time to need of ventilation. For subjects who do not record a need for ventilation but die during the treatment period, the date and time of death as recorded on the Adverse Event page will be used to calculate the time to need of ventilation.

For subjects not requiring ventilation during their treatment period and who do not die during the treatment period, the time to need of mechanical ventilation will be right censored at the date and time of treatment completion + 12 hours. For subjects who withdraw from treatment for reasons other than need for ventilation or death, the time to need of ventilation will be right censored at the date and time of withdrawal from treatment + 12 hours. The date and time of last treatment administration + 12 hours is a censoring event, should a subject be assessed as having need for ventilation after this time it will be disregarded in the analysis.

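### The event window in SAP 6.10.2.3 omits the start of the treatment period, so ventilation begun before the last dose without a ventilation-coded withdrawal is literally a non-event there but an event in 6.10.2.4

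*SAP*

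**What the plan says.** SAP 6.10.2.3 opens with a governing principle: the decision on need "during the treatment period will determine their response for use in this analysis, irrespective of whether they subsequently received ventilation". It then gives two scoring routes.

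- Route 1: a subject is an event "if they are withdrawn from treatment with the reason for withdrawal recorded as need for mechanical invasive or non-invasive ventilation or death".
- Route 2: ventilation or death "recorded in the time between last treatment administration + 12 hours will also be considered an event".

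The same paragraph defines the period of interest: "The treatment period for each subject is from the date and time of their first study treatment administration", ending 12 hours after the last dose. The Analysis paragraph then takes the proportion free of need "at any point during the study treatment period will be analysed using a logistic regression model".

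The Imputation paragraph covers subjects withdrawn for some other reason. If nothing is recorded "during the time from last treatment administration + 12 hours, they will be considered not in need of mechanical ventilation". It adds that no further imputation is required.

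Two other parts of the SAP use the Mechanical Ventilation eCRF page over a wider span. SAP 6.10.2.4 counts subjects not withdrawn for ventilation need but "who have an entry on the Mechanical Ventilation eCRF page indicating that ventilation was required during the treatment period". The 6.10.2.3 Sensitivity Analysis counts "any entry on the Mechanical Ventilation eCRF page indicating that ventilation was required", from first dose to study completion or withdrawal.

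**The concern.** Route 2 names the last dose and a 12-hour extension but not the first dose. Taken as written, it covers only the 12 hours after the last dose. The Imputation paragraph uses the same short window, so a programmer who follows the text would implement it that way. Ventilation that starts between first and last dose is then reached only through the coded withdrawal reason.

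If the code is something else, or the subject completes the course, the subject counts as free of ventilation need in the main logistic analysis. The time-to-event analysis counts the same subject as an event over the same stated period. Two consequences follow:

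- The two ventilation endpoints can report different on-treatment event counts.
- Part of any difference between the main and sensitivity logistic results could be on-treatment events that the main rule missed, although the sensitivity analysis is introduced as adding follow-up information.

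**Working it through.** The plan states no figure for this endpoint, so the check compares the rules case by case.

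**Inputs.** Routes 1 and 2 and the treatment period come from SAP 6.10.2.3, the time-to-event rule from 6.10.2.4, and the wide rule from the 6.10.2.3 Sensitivity Analysis. Times are hours from first dose. Ventilation is dated by its start. Whether ventilation that began earlier and is still running counts as recorded in the 12-hour window is not stated. A death cannot precede the last dose, so the gap concerns ventilation only.

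**Rules**, with V = ventilation start and L = last dose:

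- Literal binary: code is ventilation or death, or L ≤ V ≤ L + 12.
- Whole-period binary: code is ventilation or death, or 0 ≤ V ≤ L + 12.
- Time to event: code is ventilation, or 0 ≤ V ≤ L + 12.
- Sensitivity: code is ventilation, or any V after first dose.

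| Case | V | L | Treatment outcome | Literal | Whole period | 6.10.2.4 | Sensitivity |
|---|---|---|---|---|---|---|---|
| A | 60 | 58 | withdrawn, coded ventilation | event | event | event | event |
| B | 60 | 58 | withdrawn, coded otherwise | event | event | event | event |
| C | 60 | 72 | withdrawn, coded otherwise | **none** | event | event | event |
| D | 60 | 156 | completed | **none** | event | event | event |
| E | 160 | 156 | completed | event | event | event | event |
| F | 200 | 156 | completed | none | none | none | event |

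The literal binary rule disagrees with 6.10.2.4 in C and D only. With the window started at first dose, the two agree in all six cases. Case C fails by the express words of the Imputation paragraph. Case D fails because that paragraph addresses only withdrawn subjects and neither route reaches a completer.

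**Size of one misclassification.** The documents give no ventilation rate, so all counts below are assumptions. N = 75 per arm and two-sided 10% come from SAP 2.3 and 6.1. With a events on C21 and b on placebo:

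OR = [a/(75−a)] / [b/(75−b)], SE(log OR) = √[1/a + 1/(75−a) + 1/b + 1/(75−b)], z = log OR / SE.

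- 3 vs 9: OR = (3/72)/(9/66) = 0.31; SE = √0.4735 = 0.688; z = −1.72; p = 0.085.
- 3 vs 8 (one placebo event missed): OR = (3/72)/(8/67) = 0.35; SE = √0.4871 = 0.698; z = −1.51; p = 0.13.
- 2 vs 9 (one C21 event missed): OR = (2/73)/(9/66) = 0.20; SE = √0.6400 = 0.800; z = −2.01; p = 0.045.

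With more events, 8 vs 12 gives OR 0.63 (90% CI 0.28 to 1.40). Missing 1, 2 or 3 C21 events gives 0.54, 0.46 or 0.38. Missing 1, 2 or 3 placebo events gives 0.69, 0.78 or 0.88. The shift goes either way, depending on the arm.

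**The case against.** A reader might infer that any patient ventilated during dosing is scored as not needing ventilation. The documents do not support that. Protocol Section 5.4.1 lists ventilation need as a reason for withdrawal from study drug, Section 5.4 asks for the primary underlying reason where possible, and SAP 6.10.2.3 relies on an End of Treatment page for every treated subject. A subject withdrawn under that code is an event by route 1. A subject coded otherwise whose ventilation starts within 12 hours after the last dose is an event by route 2. The gap needs a dose given after ventilation began, together with another code or a completed course.

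A reader might also infer that the SAP deliberately excludes on-treatment ventilation. That is not supported either. Route 2 is a sentence missing one end of an interval, and the governing principle, the period definition and the Analysis paragraph all point to the whole treatment period. This is defective drafting, not a choice of endpoint.

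Further, the sensitivity analysis captures the missed cases and states that it starts at first dose. Ventilation decision, start and stop times are to be listed, so a discrepancy could be traced.

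All of this stands, and it limits the point's size. It does not remove the conflict. The short window appears in both the event rule and the non-event rule, and 6.10.2.4 makes explicit provision for subjects with a ventilation entry and no ventilation-coded withdrawal. The SAP therefore expects some. The oxygen endpoint does too: the 6.10.2.2 Imputation paragraph counts ventilation on the last dosing day separately from the withdrawal reason.

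**Conclusion.** The scoring rule is wrong as written for a narrow group: ventilation starting before the last dose, with the withdrawal coded to another reason or the course completed. For these subjects 6.10.2.3 contradicts its own period definition, its own Analysis paragraph and 6.10.2.4.

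The number affected is unknown and should be small. A material loss of power should not be inferred: the documents give neither an event rate nor a missed fraction, and they claim no power for this endpoint. What can be said is that if events are few, one misclassified subject can visibly move the odds ratio. The 3 versus 9 example was chosen near the 10% threshold and rests on assumed counts. SAP 6.10.4 treats secondary endpoints as descriptive, so crossing that threshold decides nothing formally. The correction is worth making because the endpoint is a direct clinical measure and the text can be put right before the analysis is programmed.

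**What to change.** In the definition and Imputation paragraphs of SAP 6.10.2.3, state the window as running from the first dose to the last dose plus 12 hours, whatever withdrawal reason is recorded and whether or not treatment was completed.

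Derive the binary event from the same variable as 6.10.2.4, with the same date hierarchy: the withdrawal decision time where withdrawal is for ventilation need, otherwise the start on the Mechanical Ventilation page, otherwise the time of death. Both endpoints then count the same on-treatment events, and the choice between decision and start time is settled once. The shared derivation should also say how a coded withdrawal dated later than last dose plus 12 hours is handled. Route 1 sets no time limit, whereas 6.10.2.4 disregards need assessed after that point.

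The cost is two amended sentences and one shared derivation. No new data are needed, since 6.10.2.4 and the sensitivity analysis already use the same eCRF pages.
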